**Table 2: Schedule of Assessments**

ASSESSMENTS	SCREENING	BASELINE	TREATMENT								FOLLOW-UP
	14-35 days prior to Day 1	Pre-dose  ( $\leq 3$ days prior to Day 1) (In-clinic)	Day 1  (In-clinic: Pre-Dose 1)	Day 1  (In-clinic: Dosing & Post-Dose 1)	Day 1  (In-clinic: Dosing & Post Dose 2)	Days 2-6 (At-home)	Day 7  (-1 day) (In-clinic)	Days 8-13 (At-home)	Day 14  ( $\pm 1$ day) / Early Termination  (In-clinic)	Days 15-20 (At-home)	Day 21  ( $\pm 1$ day) (In-clinic)
Administer CAD-1883 Study Drug				X  (in clinic)	X  (in clinic 4-5 hours post 1 st dose)	X	X  (in clinic 4-5 hours post 1 st dose)	X	X  (in clinic 4-5 hours post 1 st dose)		
Dispense Study Drug					X		X				
Medication Diary						X		X			
CAD-1883 PK Sample					X  CCI		X  CCI		X  CCI		X  (Anytime during visit)
TETRAS Performance Subscale 	X 	X			X 		X 		X 		X

Commercially Confidential Information

In-clinic Wearable Sensor on Upper Limb	X 	X 			X 		X 		X 		X 
---	-----------------	-----------------	--	--	-----------------	--	-----------------	--	-----------------	--	-----------------

Commercially Confidential Information

**Table 2: Schedule of Assessments**

ASSESSMENTS	SCREENING	BASELINE	TREATMENT								FOLLOW-UP	
	14-35 days prior to Day 1	Pre-dose  ( $\leq 3$ days prior to Day 1) (In-clinic)	Day 1  (In-clinic: Pre-Dose 1)	Day 1  (In-clinic: Dosing & Post-Dose 1)	Day 1  (In-clinic: Dosing & Post Dose 2)	Days 2-6 (At-home)	Day 7  (-1 day) (In-clinic)	Days 8-13 (At-home)	Day 14  ( $\pm 1$ day) / Early Termination  (In-clinic)	Days 15-20 (At-home)		
Commercially Confidential Information												
C-SSRS 		X							X		X	
Commercially Confidential Information												
AEs	X		Continuous reporting of adverse events									

\* Refer to list of abbreviations

**Schedule of Assessment Footnotes:**

 The Baseline/Pre-dose visit is the last day of the Screening period. The Baseline/Pre-dose visit must be conducted in the afternoon.

 Commercially Confidential Information

 In addition to the complete neurological exam, a focused neurological exam is conducted during the Screening visit to include full assessment of tremor per Movement Disorder Society classification criteria ([Bhatia, 2018](#)).

 Complete PE at Screening, Days 1, 7, and 14 (includes: General; HEENT; Cardiovascular; Respiratory; Abdomen; Skin; Extremities; Lymphatic system and Musculoskeletal); symptom-based PE at Baseline/Pre-dose and Day 21 Follow-up visit (includes: General, HEENT, Cardiovascular, Respiratory, Abdomen, Skin, Extremities).

 Commercially Confidential Information

 Triplicate ECG recordings, after a minimum of 5 minutes of rest in supine position: 3 consecutive recordings will be made in succession, no more than 2 minutes apart. The full set of triplicates should be completed in less than 4 minutes. These ECGs will be read by the Investigator to rule out any clinically significant findings. ECGs are to be performed prior to vital signs and blood sampling.

 Blood pressure (systolic and diastolic), heart rate, respiratory rate and oral temperature.

 Obtained prior to dosing and post dosing at 30min, 60min, 2 hours and 4 hours following the dose of study drug in the clinic. For Day 1, this is to be done Baseline/Pre-dose and 30min, 60min, and 2 hours after the first dose in the clinic, and again 30 min, 60 min, 2 hours, and 4 hours after the second dose in the clinic. There is a +/- 5-minute allowable time window for these assessments. ECG to be done before the corresponding vital sign measurements.

 For details re: orthostatic vital signs measurements, refer to Section 7.10.

 Urinalysis includes: Bilirubin, Blood, Creatinine, Glucose, Ketones, Leukocyte esterase, Microscopy, Nitrite, pH, Protein, Specific gravity, Microalbumin and Urobilinogen

 A serum pregnancy test is done at Screening only.

 A urine pregnancy test is done at Baseline/Pre-dose, Days 7, 14, and 21.

 Commercially Confidential Information

 The subject should be instructed to self-administer their first daily dose of CAD-1883 4 to 5 hours prior to the scheduled and/or anticipated dosing of the second daily dose of CAD-1883. The second daily dose of CAD-1883 should be taken in the clinic 4 to 5 hours after the first daily dose.

 Commercially Confidential Information

 Commercially Confidential Information

 Commercially Confidential Information

 TETRAS Performance Subscale assessments at Screening, Baseline/Pre-dose, Days 1, 7, 14, and 21 will be recorded via videography for central rating.

 Screening: Commercially Confidential Information

 Performed between 2-4 hours following the second dose in the clinic.

 Performed between 2-4 hours following the second daily dose in the clinic.

 Wearable sensor measurement of upper-limb tremor will be captured once at the site, at any time during Screening and Day 21.

 Wearable sensor measurements of upper limb tremor will be captured at two different times during the Baseline/Pre-dose visit.

 Wearable sensor measurements of upper limb tremor will be captured once, 2 to 4 hours following the in-clinic dose. For Day 1, this is to be done 2-4 hours after the 2nd in-clinic dose.

 At the Baseline/Pre-dose visit, the “baseline” version of the C-SSRS will be administered. This version assesses Suicidal Ideation and Suicidal Behavior during the subject’s lifetime and during a predefined period. At the Day 21 visit (and the Early Termination visit for subjects withdrawing early), the “since last visit” version will be administered. The C-SSRS does not need to be completed at the Day 14 visit if it is not an Early Termination visit. During Early Termination visit, the subject will not receive study drug, will undergo all required procedures as well as the C-SSRS.

 Both doses of study drug are to be administered in the clinic with the second dose being administered 4-5 hours after the first.

 All laboratory collections on Days 1, 7, 14 should be performed after the TETRAS-PS assessment.

## APPENDIX B: CLINICAL LABORATORY ANALYTES

### Clinical Chemistry Panel

Alanine aminotransferase	Albumin
Alkaline phosphatase	Amylase
Aspartate aminotransferase	Bicarbonate
Blood urea nitrogen	Calcium
Chloride	Creatine kinase
Creatinine	Estimated glomerular filtration rate
Commercially Confidential Information	Gamma-glutamyl transferase
Glucose	Inorganic phosphorus
Lactate dehydrogenase	Lipase
Potassium	Commercially Confidential Information
Commercially Confidential Information	Sodium
Total protein	Total and direct bilirubin
	Uric acid

### Biomarker panel for renal tubular injury

### Endocrinology

Follicle-stimulating hormone [1]	Thyroid-stimulating hormone [2]
----------------------------------	---------------------------------

[1] Postmenopausal women must have had  $\geq 365$  days of spontaneous amenorrhea, with documented follicle-stimulating hormone (FSH)  $\geq 38$  IU/mL, prior to screening. If needed, per Investigator's judgment, FSH level can be performed at Screening.

[2] An abnormal TSH level at Screening can be followed by reflex testing of thyroid hormones (T3, T4), if needed, per the Investigator's judgment.

### Hematology

Hematocrit	Hemoglobin
Platelets	Red blood cell count
White blood cell count with differentials [1]:	Red blood cell indices:
Neutrophils	MCV
Lymphocytes	MCH
Monocytes	%Reticulocytes
Eosinophils	
Basophils	

[1] Manual microscopic review is performed only if white blood cell count and/or differential values are out of reference range.

### Urinalysis

Bilirubin	Blood
Creatinine	Glucose
Ketones	Leukocyte esterase
Microscopy [1]	Microalbumin
pH	Nitrite
Specific gravity	Protein
	Urobilinogen

[1] Microscopy is performed only as needed based on positive dipstick test results.

Commercially Confidential Information

### Additional Laboratory Tests

HIV	Commercially Confidential Information
HBsAg	HCVAb [1]
Commercially Confidential Information	
Pregnancy (urine or serum according to SOA	[ Appendix A, Table 2 ])

[1] A positive result for HCVAb is acceptable provided that it was effectively treated as documented by negative results from Reflex Testing for HCV RNA (performed during Screening at the central lab or at a local or specialized lab) by either the quantitative (viral load) or qualitative (Real-Time polymerase chain reaction [PCR]) method.

## Document History

Document version	Date of availability	Note
1.0	04-Mar-2020	Final Version

## 1. Overview

This statistical analysis plan (SAP) describes the planned analysis and reporting for Cadent Therapeutics, Inc. protocol number CAD1883-201 (A Phase 2a Open-Label Study to Evaluate the Safety, Tolerability and Efficacy of CAD-1883 Oral Treatment in Adults with Essential Tremor [CADENCE-1]), dated 09-Jul-2019 Amendment 3. Reference materials for this SAP include the protocol and the accompanying sample data collection documents. Operational aspects related to data collection and timing of planned clinical assessments are not repeated in this SAP unless relevant to the planned analysis.

The structure and content of this SAP provides sufficient detail to meet the requirements identified by the Food and Drug Administration (FDA), European Medicines Agency (EMA), and International Conference on Harmonization (ICH) of Technical Requirements for Registration of Pharmaceuticals for Human Use: Guidance on Statistical Principles in Clinical Trials. All work planned and reported for this SAP will follow internationally accepted guidelines, published by the American Statistical Association and the Royal Statistical Society, for statistical practice.

The planned analyses identified in this SAP may be included in clinical study reports (CSRs), regulatory submissions, or future manuscripts.

Commercially Confidential Information

## 2. Study Objectives and Endpoints

### 2.1. Study Objectives

#### 2.1.1. Primary Objective

The primary objective is to evaluate the safety and tolerability of twice-daily oral dosing of CAD-1883 over 14 days of treatment in adult subjects with Essential Tremor (ET).

#### 2.1.2. Secondary Objectives

The secondary objectives are to evaluate the efficacy of twice-daily oral dosing of CAD-1883 over 14 days of treatment as measured by:

- The Essential Tremor Rating Assessment Scale (TETRAS)-performance subscale (PS) total score change from Baseline to Day 14
- TETRAS-PS upper limb subscale score change from Baseline to Day 14
- Change from Baseline to Day 14 in upper limb tremor severity, mean amplitude, and mean frequency, measured in the clinic using a wearable sensor

Commercially Confidential Information

Commercially Confidential Information

## **2.2. Study Endpoints**

### **2.2.1. Safety Endpoints**

The primary safety endpoint of the study is the occurrence and severity of treatment emergent AEs (TEAEs).

### **2.2.2. Efficacy Endpoints**

#### **2.2.2.1. Primary Efficacy Endpoint**

Not applicable. The primary endpoint of this study is safety and tolerability.

#### **2.2.2.2. Secondary Efficacy Endpoints**

The secondary efficacy endpoints of this study are:

- TETRAS-PS total score change from Baseline to Day 14
- TETRAS-PS upper limb subscale score change from Baseline to Day 14

Commercially Confidential Information

- Change from Baseline to Day 14 in upper limb tremor severity, mean amplitude, and mean frequency, measured in the clinic using a wearable sensor
- Change from Baseline in mean frequency of tremor in arm on table posture, measured in the clinic using a wearable sensor

Commercially Confidential Information

### **3. Overall Study Design and Plan**

#### **3.1. Overall Design**

This is an open-label study designed to evaluate the safety, tolerability, and efficacy of CAD-1883 administered twice daily orally to adult subjects with ET. The diagnosis of ET must be established by the Principal Investigator at Screening based on the Movement Disorder Society (MDS) criteria with a documented severity of tremor based on the clinician-administered TETRAS-PS.

Commercially Confidential Information

Subjects will undergo a screening period of a minimum of 14 days up to a maximum of 35 days in which the subject will washout from prior Commercially Confidential medications, to allow the effects of previous medication(s) Information CCI to be eliminated. Subjects will return to the site for further assessments on Day 7 (-1 day) and Day 14 ( $\pm 1$  day) and a Follow-up visit (Day 21 [ $\pm 1$  day]). The wearable sensor measurements of upper limb tremor assessments will be completed in the clinic once at any time during the Screening visit and at two different times during the Baseline/Pre-dose site visit.

Commercially Confidential Information

subjects will have the option to complete at-home assessments of tremor using the wearable sensor

Commercially Confidential Information

#### **3.2. Sample Size and Power**

Up to 30 subjects will be enrolled. No formal statistical power analysis was conducted.

#### **3.3. Study Population**

This study includes subjects between 18 and 75 years old, inclusive, with a history of tremor for at least 3 years.

#### **3.4. Treatments Administered**

The study will be open-label consisting of 1 treatment group receiving 300 mg twice-daily oral dosing of CAD-1883 for a treatment period of 14 days. Dose intervals on Days 1, 7 and 14 are changed from the protocol amendment 1 through 3. Subjects enrolled under the protocol amendment 1 take the first dose of CAD-1883 300 mg (3 capsules of 100 mg each) at the site, 2nd dose are taken 8 hours ( $\pm 2$  hours) after the first dose. On Days 7 and 14, the subjects are instructed to ingest the first daily dose of CAD-1883 of 300 mg at home. The second daily dose are taken in the clinic 8 hours ( $\pm 2$  hours) after the first daily dose. For subjects enrolled under the protocol amendment 2 and 3 the first dose on Day 1 is taken in clinic and the second dose is taken 4 to 5 hours later. On Days 7 and 14, the first daily dose is taken at home and the second daily dose is taken in the clinic 4 to 5 hours later.

#### **3.5. Method of Assigning Subjects to Treatment Groups**

There is 1 treatment group. Eligible subjects are enrolled sequentially. There was no randomization, blinding, or stratification employed in this study.

#### **3.6. Blinding and Unblinding**

This is an open-label study with no blinding.

### **3.7. Schedule of Events**

A detailed schedule of events for the study is provided in [Table 1](#).

**Table 1: Schedule of Events**

ASSESSMENTS	SCREENING	BASELINE	TREATMENT								FOLLOW-UP
	14-35 days prior to Day 1	Pre-dose  ( $\leq 3$ days prior to Day 1) (In-clinic)	Day 1  (In-clinic: Pre-Dose 1)	Day 1  (In-clinic: Dosing & Post-Dose 1)	Day 1  (In-clinic: Dosing & Post Dose 2)	Days 2-6 (At-home)	Day 7  (-1 day) (In-clinic)	Days 8-13 (At-home)	Day 14  ( $\pm 1$ day) / Early Termination  (In-clinic)	Days 15-20 (At-home)	
Eligibility Check	X	X									
Informed Consent	X										
Inclusion/Exclusion Criteria	X	X									
Demographics	X										
Medical History	X										
Neurological Exam	X 	X					X		X		X
Physical Exam	X	X 	X				X		X		X 
Height	X										
Weight CCI	X 								X		X
12-lead ECG 	X	X	X 	X  (30 min, 60 min, 2 hours post 1 st dose)	X  (30 min, 60 min, 2 & 4 hours post 2 nd dose)		X  (30 min, 60 min, 2 & 4 hours post 2 nd dose)		X  (30 min, 60 min, 2 & 4 hours post 2 nd dose)		X
Vital Signs 	X	X	X 	X  (30 min, 60 min, 2 hours post 1 st dose)	X  (30 min, 60 min, 2 & 4 hours post 2 nd dose)		X  (30 min, 60 min, 2 & 4 hours post 2 nd dose)		X  (30 min, 60 min, 2 & 4 hours post 2 nd dose)		X

ASSESSMENTS	SCREENING	BASELINE	TREATMENT								FOLLOW-UP
	14-35 days prior to Day 1	Pre-dose  (≤ 3 days prior to Day 1) (In-clinic)	Day 1  (In-clinic: Pre-Dose 1)	Day 1  (In-clinic: Dosing & Post-Dose 1)	Day 1  (In-clinic: Dosing & Post Dose 2)	Days 2-6 (At-home)	Day 7  (-1 day) (In-clinic)	Days 8-13 (At-home)	Day 14  (±1 day) / Early Termination  (In-clinic)	Days 15-20 (At-home)	Day 21  (±1 day) (In-clinic)
Orthostatic VS 	X (3 times, 15-20 min apart)	X		X (2-4 hours post 1 st dose)	X (2-4 hours post 2 nd dose)		X (2-4 hours post dose)		X (2-4 hours post dose)		X
Clinical Chemistry	X	X			X 		X 		X 		X
Hematology	X	X			X 		X 		X 		X
Urinalysis 	X	X			X 		X 		X 		X
Biomarker panel for renal tubular injury		X			X 		X 		X 		X
Pregnancy Test	X 	X 					X 		X 		X 
HIV, CCI HBsAg, HCVAb	X										
TSH – FSH (optional for females only; if needed)	X										

Commercially Confidential Information

Commercially Confidential Information

Commercially Confidential Information

ASSESSMENTS	SCREENING	BASELINE	TREATMENT								FOLLOW-UP
	14-35 days prior to Day 1	Pre-dose  ( $\leq 3$ days prior to Day 1) (In-clinic)	Day 1  (In-clinic: Pre-Dose 1)	Day 1  (In-clinic: Dosing & Post-Dose 1)	Day 1  (In-clinic: Dosing & Post Dose 2)	Days 2-6 (At-home)	Day 7  (-1 day) (In-clinic)	Days 8-13 (At-home)	Day 14  ( $\pm 1$ day) / Early Termination  (In-clinic)	Days 15-20 (At-home)	Day 21  ( $\pm 1$ day) (In-clinic)
Administer CAD-1883 Study Drug				X  (in clinic)	X  (in clinic 4-5 hours post 1 st dose)	X	X  (in clinic 4-5 hours post 1 st dose)	X	X  (in clinic 4-5 hours post 1 st dose)		
Dispense Study Drug					X		X				
Medication Diary						X		X			
CAD-1883 PK Sample					X  CCI		X  CCI		X  CCI		X  (Anytime during visit)
TETRAS Performance Subscale 	X 	X			X 		X 		X 		X

Commercially Confidential Information

In-clinic Wearable Sensor on Upper Limb	X 	X 			X 		X 		X 		X 
---	-----------------	-----------------	--	--	-----------------	--	-----------------	--	-----------------	--	-----------------

ASSESSMENTS	SCREENING	BASELINE	TREATMENT								FOLLOW-UP
	14-35 days prior to Day 1	Pre-dose  ( $\leq 3$ days prior to Day 1) (In-clinic)	Day 1  (In-clinic: Pre-Dose 1)	Day 1  (In-clinic: Dosing & Post-Dose 1)	Day 1  (In-clinic: Dosing & Post Dose 2)	Days 2-6 (At-home)	Day 7  (-1 day) (In-clinic)	Days 8-13 (At-home)	Day 14  ( $\pm 1$ day) / Early Termination  (In-clinic)	Days 15-20 (At-home)	Day 21  ( $\pm 1$ day) (In-clinic)

Commercially Confidential Information

Commercially Confidential Information

C-SSRS 		X							X		X
----------------------	--	---	--	--	--	--	--	--	---	--	---

Commercially Confidential Information

AEs	X	Continuous reporting of adverse events
-----	---	--

\* Refer to list of abbreviations

**Schedule of Assessment Footnotes:**

 The Baseline/Pre-dose visit is the last day of the Screening period. The Baseline/Pre-dose visit must be conducted in the afternoon.

 Commercially Confidential Information

 In addition to the complete neurological exam, a focused neurological exam is conducted during the Screening visit to include full assessment of tremor per Movement Disorder Society classification criteria ([Bhatia, 2018](#)).

 Complete PE at Screening, Days 1, 7, and 14 (includes: General; HEENT; Cardiovascular; Respiratory; Abdomen; Skin; Extremities; Lymphatic system and Musculoskeletal); symptom-based PE at Baseline/Pre-dose and Day 21 Follow-up visit (includes: General, HEENT, Cardiovascular, Respiratory, Abdomen, Skin, Extremities).

 Commercially Confidential Information

 Triplicate ECG recordings, after a minimum of 5 minutes of rest in supine position: 3 consecutive recordings will be made in succession, no more than 2 minutes apart. The full set of triplicates should be completed in less than 4 minutes. These ECGs will be read by the Investigator to rule out any clinically significant findings. ECGs are to be performed prior to vital signs and blood sampling.

 Blood pressure (systolic and diastolic), heart rate, respiratory rate and oral temperature.

 Obtained prior to dosing and post dosing at 30min, 60min, 2 hours and 4 hours following the dose of study drug in the clinic. For Day 1, this is to be done Baseline/Pre-dose and 30min, 60min, and 2 hours after the first dose in the clinic, and again 30 min, 60 min, 2 hours, and 4 hours after the second dose in the clinic. There is a +/- 5-minute allowable time window for these assessments. ECG to be done before the corresponding vital sign measurements.

 For details re: orthostatic vital signs measurements, refer to Section 7.10.

 Urinalysis includes: Bilirubin, Blood, Creatinine, Glucose, Ketones, Leukocyte esterase, Microscopy, Nitrite, pH, Protein, Specific gravity, Microalbumin and Urobilinogen

 A serum pregnancy test is done at Screening only.

 A urine pregnancy test is done at Baseline/Pre-dose, Days 7, 14, and 21.

 Commercially Confidential Information

 The subject should be instructed to self-administer their first daily dose of CAD-1883 4 to 5 hours prior to the scheduled and/or anticipated dosing of the second daily dose of CAD-1883. The second daily dose of CAD-1883 should be taken in the clinic 4 to 5 hours after the first daily dose.

Commercially Confidential Information

 TETRAS Performance Subscale assessments at Screening, Baseline/Pre-dose, Days 1, 7, 14, and 21 will be recorded via videography for central rating.

 Screening: Commercially Confidential Information

 Performed between 2-4 hours following the second dose in the clinic.

 Performed between 2-4 hours following the second daily dose in the clinic.

 Wearable sensor measurement of upper-limb tremor will be captured once at the site, at any time during Screening and Day 21.

 Wearable sensor measurements of upper limb tremor will be captured at two different times during the Baseline/Pre-dose visit.

 Wearable sensor measurements of upper limb tremor will be captured once, 2 to 4 hours following the in-clinic dose. For Day 1, this is to be done 2-4 hours after the 2nd in-clinic dose.

 At the Baseline/Pre-dose visit, the “baseline” version of the C-SSRS will be administered. This version assesses Suicidal Ideation and Suicidal Behavior during the subject’s lifetime and during a predefined period. At the Day 21 visit (and the Early Termination visit for subjects withdrawing early), the “since last visit” version will be administered. The C-SSRS does not need to be completed at the Day 14 visit if it is not an Early Termination visit. During Early Termination visit, the subject will not receive study drug, will undergo all required procedures as well as the C-SSRS.

 (Protocol Amendment 3) Both doses of study drug are to be administered in the clinic with the second dose being administered 4-5 hours after the first.

 All laboratory collections on Days 1, 7, 14 should be performed after the TETRAS-PS assessment.

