On Days 1, 7, 14, and 21, subjects will undergo safety monitoring consisting of reporting of AEs or SAEs, collection of vital signs including orthostatic vital signs, undergo a 12-lead ECG, and collection of urine for urinalysis and a composite biomarker panel for renal tubular injury, and blood for hematology, clinical chemistry, and plasma drug level. On Day 1, 7 and 14, all urine and blood collections should take place after the TETRAS-PS assessment. Assessment of rating scales and upper limb wearable sensor measurements will also be performed.

On Day 7 and Day 14, the subjects are instructed to ingest the first daily dose of CAD-1883 of 300 mg (3 capsules of 100 mg each) at home 4 to 5 hours prior to the scheduled and/or anticipated dosing of the second daily dose of CAD-1883. The second daily dose of CAD-1883 300 mg (3 capsules of 100 mg each) will be taken in the clinic, under the supervision of study staff, 4 to 5 hours after the first daily dose.

Commercially Confidential Information

subjects will have the option to complete at-home assessments of tremor using the wearable sensor.

Commercially Confidential Information

Commercially Confidential Information

Upon completion of the 14-day treatment period, subjects will return to the site for the Day 21 Follow-up visit, approximately 7 days ( $\pm 1$  day) after the last dose of study drug was administered.

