## **9.2. Clinical Laboratory Evaluations**

Screening and safety laboratory tests will be performed at Screening, Pre-dose, Day 1, Day 7, Day 14, and at follow-up on Day 21. All laboratory test results will be summarized descriptively by study visit for the Safety Population overall and by cohort as both observed values and change from baseline values for each parameter. Categorical urinalysis results will be summarized using frequencies by study visit and cohort. Levels of composite biomarker panel for renal tubular injury will also be summarized by study visit and listed.

Shifts from baseline for clinical laboratory values below, within, or above the normal range will be provided for hematology and chemistry results by study visit. See Section 6.1.1 for the definition of baseline. Clinically significant abnormal findings will be reported as AEs. Abnormal laboratory results will be listed.

Pregnancy test results will be listed.

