## **9.7 Kidney safety Composite Measure Biomarker**

The following 6 kidney safety composite measure biomarkers were tested using urine sample: uCreatine (uCr), uClusterin (uCLU) , uCystatin-C (uCysC), uKidney Injury Molecule-1 (uKIM-1), u N-Acetyl-beta-D-Glucosaminidase (uNAG), Neutrophil Gelatinase-Associated Lipocalin (uNGAL) and uOsteopontin (uOPN). Measured concentration is first normalized by dividing it by the concentration of uCR at the same timepoint. The fold change from baseline at a given timepoint is then calculated using the normalized concentration at a time point divided by the normalized concentration at baseline. For example, the normalized uCysC concentration at a given timepoint is calculated as the concentration of CysC at that timepoint divided by the concentration of uCr at the same timepoint. The uCysC fold change from baseline at a given timepoint is calculated as the normalized CysC concentration at a given timepoint divided by the normalized uCysC concentration at baseline. Similar calculations apply to other composite measures.

Commercially Confidential Information

Commercially Confidential Information

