### 13.3. Safety Data

**Table 6: Safety Data**

Number	Population	Title
Table 14.3.1.1	Safety	Summary of Adverse Events
Table 14.3.1.2	Safety	Incidence of Treatment Emergent Adverse Events by SOC and PT
Table 14.3.1.3	Safety	Incidence of Treatment Emergent Adverse Events by SOC, and PT, and Maximum Severity

Number	Population	Title
Table 14.3.1.4	Safety	Incidence of Treatment Emergent Adverse Events by SOC, PT, and Relationship
Table 14.3.2.1	Safety	Incidence of TEAEs Leading to Withdrawal of Study Drug by SOC and PT
Table 14.3.2.2	Safety	Incidence of Serious Adverse Events by SOC and PT
Table 14.3.3.1	Safety	Listing of Adverse Events Leading to Study Drug Discontinuation
Table 14.3.3.2	Safety	Listing of Serious Adverse Events
Table 14.3.3.3	Safety	Listing of Deaths
Table 14.3.4.1	Safety	Abnormal Laboratory Results
Table 14.3.5.1.1	Safety	Summary of Hematology Laboratory Results by Study Visit
Table 14.3.5.1.2	Safety	Shift from Baseline in Hematology Laboratory Results by Study Visit
Table 14.3.5.2.1	Safety	Summary of Serum Chemistry Laboratory Results by Study Visit
Table 14.3.5.2.2	Safety	Shift from Baseline in Serum Chemistry Laboratory Results by Study Visit
Table 14.3.5.3.1	Safety	Summary of Quantitative Urinalysis Laboratory Results by Study Visit
Table 14.3.5.3.2	Safety	Shift from Baseline in Quantitative Urinalysis Laboratory Results by Study Visit
Table 14.3.5.3.3	Safety	Summary of Qualitative Urinalysis Laboratory Results by Study Visit
Table 14.3.5.4.1	Safety	Summary of Quantitative Biomarker Panel for Renal Injury Results by Study Visit
Table 14.3.5.4.2	Safety	Geometric Mean (GM) Composite Measure (CM) on Quantitative Biomarker Panel for Renal Tubular Injury Results by Study Visit
Table 14.3.6.1.1	Safety	Summary of Vital Signs by Study Visit
Table 14.3.6.1.2	Safety	Shift from Baseline in Vital Signs by Study Visit
Table 14.3.6.1.3	Safety	Summary of Orthostatic Vital Signs by Study Visit
Table 14.3.6.1.4	Safety	Shift from Baseline in Orthostatic Vital Signs by Study Visit

Number	Population	Title
Table 14.3.6.1.5	Safety	Summary of Orthostatic Vital Signs Shift from Baseline Categories by Study Visit
Table 14.3.6.1.6	Safety	Summary of Orthostatic Hypotension by Study Visit
Table 14.3.6.2.1	Safety	Summary of 12-Lead Electrocardiogram by Study Visit
Table 14.3.6.2.2	Safety	Summary of 12-Lead Electrocardiogram Interpretation by Study Visit
Table 14.3.6.2.3	Safety	Summary of QTcF Values by Study Visit

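### Urine albumin and urine creatinine are summarised separately, so urine dilution adds noise to the albumin summary; an albumin-to-creatinine ratio would remove it at almost no cost

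*SAP*

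**What the plan says.** The urinalysis footnote to the schedule, the same in the protocol and the SAP, lists creatinine and microalbumin as separate analytes: "Urinalysis includes: Bilirubin, Blood, Creatinine, Glucose, Ketones, Leukocyte esterase, Microscopy, Nitrite, pH, Protein, Specific gravity, Microalbumin and Urobilinogen". Protocol Appendix B lists the same two. Urinalysis is marked at all six clinic visits, and SAP 9.2 agrees: "Screening and safety laboratory tests will be performed at Screening, Pre-dose, Day 1, Day 7, Day 14, and at follow-up on Day 21".

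For analysis, SAP 9.2 states: "All laboratory test results will be summarized descriptively by study visit". It does so "as both observed values and change from baseline values for each parameter". For results that are not numeric, "Categorical urinalysis results will be summarized using frequencies by study visit and cohort".

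The table list gives Table 14.3.5.3.1, "Summary of Quantitative Urinalysis Laboratory Results by Study Visit", and a matching shift table, 14.3.5.3.2. Both reuse the hematology shells: n, mean (SD), median and range in one, low/normal/high shifts in the other. Neither has a normalised column, and the visible derived variables in SAP 6.1.8 include no albumin-to-creatinine ratio.

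SAP 9.7 handles the tubular-injury biomarkers differently: "Measured concentration is first normalized by dividing it by the concentration of uCR at the same timepoint". Fold change from baseline is then computed on the normalised value, and Table 14.3.5.4.1 shows measured and normalised results. Albumin is not in that panel.

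**The concern.** The concentration of any substance in a spot urine sample depends on how much water is in that sample. The SAP accepts this for the tubular-injury biomarkers and corrects for it. It makes no such correction for albumin, although the divisor it would need sits in the same urinalysis panel, and it gives no reason for the difference.

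The trial watches the kidney closely. It has a dedicated biomarker panel, creatinine-based exclusion limits (exclusion criterion 13) and a composite figure with a threshold. A reader of the urinalysis tables will look at albumin with that in mind. With one arm and up to 30 subjects, there is no control group against which to judge whether a movement in raw albumin reflects the kidney or the water content of the urine.

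**Working it through.** The plan states no figure on this point, so there is nothing to reproduce. The check has three steps.

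**1. Is the ratio planned anywhere visible?** I looked at the analyte lists (schedule footnote 10, Protocol Appendix B), SAP 6.1.8, 9.2 and 9.7, the table list in SAP 13.3, and the shells. No ratio appears. The urinalysis and renal tables run 14.3.5.3.1, .3.2, .3.3, .4.1, .4.2 without a missing number, so no hidden table sits among them.

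**2. What dilution does to a raw fold change.** Let A be the fold change from baseline in the albumin-to-creatinine ratio and C the fold change in urine concentration, as carried by urine creatinine. Then

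raw albumin fold change = A × C.

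| True ratio change A | Concentration change C | Raw albumin A × C | Ratio shows |
|---|---|---|---|
| 1.00 | 2.00 | 2.00 | 1.00 |
| 2.00 | 0.50 | 1.00 | 2.00 |
| 1.00 | 1.18 | 1.18 | 1.00 |
| 1.50 | 1/1.18 = 0.85 | 1.27 | 1.50 |

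Row 1 is a false signal and row 2 a hidden effect. The 1.18 in rows 3 and 4 is borrowed from the threshold in the Figure 14.5 programming note. It belongs to the tubular-injury composite, not to albumin, and serves here only as a familiar scale.

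**3. What random dilution does to precision.** If the log ratio change and the log concentration change are independent,

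SD(raw log change) = √(SD_ratio² + SD_dilution²),

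and the 95% limits of a geometric mean fold change are the estimate divided and multiplied by exp(1.96 × SD / √n).

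The documents give neither SD. Both are assumed here, with n = 30:

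| SD_ratio | SD_dilution | SD of raw change | 95% limit factor |
|---|---|---|---|
| 0.5 | 0 (ratio used) | 0.50 | 1.20 |
| 0.5 | 0.4 | 0.64 | 1.26 |
| 0.5 | 0.6 | 0.78 | 1.32 |
| 0.5 | 0.8 | 0.94 | 1.40 |
| 0.7 | 0 (ratio used) | 0.70 | 1.28 |
| 0.7 | 0.4 | 0.81 | 1.33 |
| 0.7 | 0.6 | 0.92 | 1.39 |
| 0.7 | 0.8 | 1.06 | 1.46 |

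Example: √(0.5² + 0.4²) = √0.41 = 0.64, and exp(1.96 × 0.64 / √30) = 1.26. Under these assumptions the limits for raw albumin are wider than those for the ratio in every row. How much wider depends entirely on the assumed SDs.

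**The case against.** **The sampling times are broadly matched.** The protocol says: "On Day 1, 7 and 14, all urine and blood collections should take place after the TETRAS-PS assessment". A reader might infer that urine is systematically more or less dilute at treatment visits than at Baseline. The documents do not support that. Schedule footnote 1 places the Baseline visit in the afternoon. On treatment days the TETRAS-PS falls 2 to 4 hours after a second dose that itself follows the first by 4 to 5 hours, so urine is collected at least 6 hours after the morning dose (4 + 2), which will usually also be the afternoon. Footnote 2, attached to Baseline and every later clinic visit, is blacked out, so further visit conditions may exist. This objection stands. What remains is ordinary visit-to-visit variation in dilution.

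**Microalbumin may not be numeric.** The quantitative shells name no parameters, and there is a separate qualitative table, 14.3.5.3.3. This stands too. If microalbumin is reported as a category, it goes into a frequency table, still uncorrected, and no ratio can be formed. The fix has to be conditional.

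**Renal safety is covered elsewhere.** The normalised tubular panel, serum creatinine and estimated glomerular filtration rate are all there, and specific gravity lets a reader look for dilution subject by subject. This limits the stakes, but none of these corrects the albumin summary.

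**Redaction.** Parts of SAP 6.1.8, SAP 9.7 and Appendix B are blacked out, so a ratio cannot be wholly excluded. The unbroken table numbering makes a planned ratio table unlikely.

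**Nothing is lost.** Raw urinalysis values are listed, so a ratio could be computed later if they are numeric. That is correct, but it would then be a post hoc choice.

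**Conclusion.** The point holds as a modest gap in a descriptive safety summary. On the visible text, albumin is the urinary marker of renal effect that the SAP singles out neither for normalisation nor for a reason to omit it, although the SAP uses the needed method one section later.

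The mechanism is exact arithmetic. Its size in this trial is not known, because the documents give no variability for albumin or urine concentration, and the precision figures above are illustrations only. A reader might go on to translate them into lost power or extra subjects needed. That does not apply: these laboratory results are summarised descriptively and the trial has no power calculation. Nor should the point be read as saying that renal safety as a whole is uncorrected. It concerns albumin, and the primary endpoint of treatment-emergent adverse events is untouched.

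The conclusion assumes that microalbumin is reported numerically, that no ratio lies under the redactions, and that urine creatinine is a fair measure of urine concentration in these subjects. SAP 9.7 already relies on the last of these.

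**What to change.** Where microalbumin is reported numerically:

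- In SAP 6.1.8, define urine albumin-to-creatinine ratio = microalbumin / urine creatinine, both from the same sample. State how results below the limit of quantification enter it, since a geometric mean needs positive values.
- In Table 14.3.5.3.1, add the ratio by visit, with geometric mean and fold change from baseline, following SAP 9.7.
- In Table 14.3.5.3.2, show shifts on the ratio and name the reference range used; the visible documents give none.
- State that the ratio is the albumin measure to be interpreted, and keep raw microalbumin and creatinine in Listing 16.2.8.1.3.

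If microalbumin is only categorical, say so in SAP 9.2 and note that the frequencies are not corrected for dilution.

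The cost is one derived variable and a few table rows from data already collected. No new sample, visit or subject is needed.
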